Study Protocol

Timing Personalized Feedback after Alcohol Health Education

NCT04453007

June 23, 2022

Principal Investigator:

[name].

Description and Purpose of the Project

Heavy episodic alcohol use within the college student population is widespread, creating problems for student drinkers, their peers, and their institutions. Negative consequences from heavy alcohol use can be mild (e.g., hangovers, missed classes), to severe (e.g., assault, even death). Although online interventions targeting college student drinking reduce alcohol consumption and associated problems, they are not as effective as in-person interventions. Online interventions are cost-effective, offer privacy, reduce stigma, and may reach individuals who would otherwise not receive treatment. In a recently completed randomized, controlled trial, an emailed booster with personalized feedback improved the efficacy of a popular online intervention (Braitman & Henson, 2016). A second randomized, controlled trial confirmed efficacy for students of legal drinking age for a longer timeline (Braitman & Lau-Barraco, 2018). Although promising, the booster incorporated in the study needs further empirical refinement. In particular, it is not known if boosters are most efficacious if administered when the intervention effect is still strong, or as the intervention effect begins to wane. Thus, an empirical question is the optimal timing of the second dose.. [Findings from Study 2 should elucidate students' peak receptivity by identifying the delivery timing with the highest efficacy.]

Primary Aims

The current project seeks to build on past progress by further developing and refining the booster. In particular, to identify the most efficacious timing for sending the feedback. The content will be similar across conditions, but will be disseminated at different times to identify the most impactful timeline. This study compares booster delivery at 2 weeks after the intervention (known to be effective; Braitman & Henson, 2016; Braitman & Lau-Barraco, 2018) to delivery at week 14 (known to be the window when intervention effects wane based on meta-analysis; Carey et al., 2012), and delivery at weeks 6 or 10 (the midpoints between these two empirically-supported times). A fifth group will receive the booster at all four delivery times as a repeated administration comparison. Finally, an intervention-only control group will also be used. Thus, there will be 6 study conditions: those who receive the emailed feedback 2, 6, 10, or 14 weeks after baseline, or at all of those times, or not at all (control). Thus, the aim of the current study is to identify optimal timing for sending the tailored booster feedback via booster email.

Participant population

Eligible participants must 1) have consumed at least 1 drink containing alcohol within 2 weeks prior to participation; 2) be between the ages of 18-24 years old; 3) must be an undergraduate student at the host institution; and 4) [prior to 3/29/21] were enrolled in classes that were in-person or hybrid [had an in-person component] OR [after 3/29/21] have consumed alcohol in person with others in the past 30 days. Note that this last criterion was developed in response to the COVID-19 global pandemic. Attending classes in person was viewed as a proxy for willingness to gather with others in person, potentially drinking with others in person as well. However, study enrollment was slow, and relatively few students were taking classes in person. Thus, we decided to switch to a more direct assessment of social drinking, including enrolling

online students in the study if they reported drinking alcohol with others in person. Power analyses were conducted using Monte Carlo simulation methods within Mplus (version 5.21, Muthén & Muthén). Effect sizes, variance, and covariances used were based on data from a preliminary study with similar eligibility criteria using the same booster content (Braitman & Henson, 2016; Braitman & Lau-Barraco, 2018). We estimated a retention rate of 76%, the average reported in a meta-analysis of RCTs assessing alcohol interventions for first-year college students (Scott-Sheldon et al., 2014). Monte Carlo simulation methods indicated that for the effect size expected ($b = 6.57$, $\beta = 0.537$) and for the expected 24% attrition, a sample size of $N = 180$ total students should yield sufficient power (.80+) to detect booster effects.

Recruitment Procedure

An email describing the study is sent to undergraduate students at ODU ages 18-24 who have enrolled in at least 1 credit hour, and includes a link to a screener survey. In addition to eligibility criteria (age, student status, if they drink with others, and alcohol consumed) additional irrelevant questions are included in the screener survey to discourage ineligible participants from re-taking the screener survey with different answers. Eligible participants can provide their contact information (name, email, and phone number) and are linked to Calendly to schedule their participation in the baseline protocol via Zoom.

Study Procedure

Emerging adult college drinkers are recruited via email as described above. After completing the screener to verify eligibility, participants schedule their participation time through an online time management system (Calendly). They receive an email reminder from the Calendly system 24 hours before their assigned timeslot. After participating in the fully remote baseline session via Zoom, participants are be paid \$20. They are also be invited to complete follow-up surveys for additional money. Participants are invited to complete 1-, 3-, 6-, and 9-month assessments, and receive \$10 for each completed follow-up survey. As an additional incentive, participants who complete all assessments will be given a \$10 bonus (yielding a \$70 total for the study if all follow-ups are completed). All monetary compensation is provided via online gift card to Amazon.

Baseline: Participants sign on to Zoom via the link provided during their assigned timeslot. Upon signing into the Zoom meeting, the research assistants provide a link (using the chat function) directing them to a Qualtrics survey. Participants read and view videos of the study procedures on the first page of this website. The videos have been created in Powtoon, using voiceover and images that are not related to a specific gender or race/ethnicity. After reviewing the videos, participants are provided with the informed consent document (on a subsequent page of the survey), will have the opportunity to ask questions during the live Zoom session with the research assistant. After consenting to participate, they are directed to complete the baseline survey (approximately 30-45 minutes). All participants will complete this computerized survey that assesses alcohol use, alcohol-related problems, protective behavioral strategies for drinking and their perceived effectiveness, motives and expectancies for alcohol use, anonymized social network characteristics, context of their most recent drinking occasion, marijuana and tobacco use, COVID-19 experiences, internalizing symptoms, and demographic

measures. Through a mechanism of the survey, participants are randomly assigned to one of six possible conditions regarding the timing of receiving emailed personalized feedback about their alcohol use. After completing the initial assessment, participants are then be directed to navigate through the eCHECKUP TO GO program (San Diego State University Research Foundation, 2018) until it is completed (approximately 20-30 minutes).

Subsequent assessments: Approximately 1, 3, 6, and 9 months after the initial assessment, researchers send each participant an email reminding them to complete the follow-up assessment. This email includes a link to an online follow-up survey that assesses alcohol use, related problems, protective behavioral strategies for drinking and their perceived effectiveness, anonymized social network characteristics, context of their most recent drinking occasion, and marijuana and tobacco use. If participants provide additional ways to contact them during the baseline survey (a second email address, a phone number to text), these methods are also used to send the link to the follow-up surveys.

Boosters: After the intervention, participants receive an additional email from the researcher, depending on their study condition. For five study conditions, these emails contain personalized normative feedback about alcohol use as well as feedback about harm reduction strategies, serving as a booster to the original intervention. Baseline data are used to provide students with normative information (e.g., typical drinking among ODU students who are male/female depending on the gender of the recipient), and reminders of protective behavioral strategies they can use to reduce drinking-related harm (separated by strategies they have reported using recently versus those they might consider trying). This is received at 2 weeks, 6 weeks, 10 weeks, or 14 weeks after baseline for study conditions 1-4 respectively. This is received at all of those times for some participations (the 5th study condition). Participants in the control condition (6th study condition) do not receive any feedback via email.

Measures

The same measures are included in baseline and the follow-up surveys:

Participants' **alcohol use** is assessed using a modified version of the Daily Drinking Questionnaire for the past 30 days (Collins et al., 1985). Additionally, participants describe specific aspects regarding their drinking in the past 30 days (e.g., highest consumption in a single day). **Descriptive Norms** are assessed by modifying the DDQ to reflect their expectations for typical male students at the same institution, typical female students at the same institution, and close friends. **Injunctive Norms** are assessed using 10 items (Carey et al., 2010). **Alcohol-related problems** are assessed using the 24-item Brief Young Adult Alcohol Consequences Questionnaire (BYAACQ; Kahler et al., 2005). **Protective behavioral strategy** (PBS) use is assessed using Sugarman and Carey's (2007) Strategy Questionnaire. **Alcohol expectancies** are assessed using the Comprehensive Effects of Alcohol questionnaire (CEOA; Fromme et al., 1993). **Motives for alcohol use** are assessed using the Drinking Motives Questionnaire (DMQ; Cooper, 1994). **Alcohol beliefs** about how salient alcohol use is to college life are assessed using the College Life Alcohol Salience Scale (CLASS; Osberg et al., 2010). Questions about their **Social media use** were created by the researcher. **Social network** and affiliated characteristics are assessed using the adapted version (DeMartini et al., 2013) of the Brief Important People

Interview (BIPI; Zywiak et al., 2002). **Marijuana use** is assessed using recommended best practices (Prince, 2019), and **tobacco use** is assessed using items created by the researcher. **Perceived Importance of Marijuana to the College Experience Scale** (PIMCES; Pearson et al., 2017) is used to assess how salient marijuana is to college life. Questions about participants' experiences with the COVID-19 pandemic were created by the researchers. **Symptoms of depression** are assessed using the short version of the Center for Epidemiological Studies Depression scale (CESD-10; Andresen et al., 1994), altered to reflect the past 30 days. **Anxiety** is assessed using the Generalized Anxiety Disorder 7 (GAD-7; Spitzer et al., 2006), modified to reflect the past 30 days. **Stress** is assessed using the psychological vulnerability subscale of the Perceived Stress Scale – Revised (PSS-R; Wickrama et al., 2013), modified to reflect the past 30 days. **COVID-19-specific stress** is assessed using the COVID-19 Stress measure (Ellis et al., 2020). **Demographics and general information** are assessed during the initial assessment only. Participants report their age, race, sex, Greek affiliation (i.e., membership in fraternities or sororities), GPA, class standing, athletic status student status (full- versus part-time), residential status, relationship status, sexual identity, height, and weight (for blood alcohol content calculations).

References

- Andresen, E. M., Malmgren, J. A., Carter, W. B., & Patrick, D. L. (1994). Screening for depression in well older adults: Evaluation of a short form of the CES-D. *American Journal of Preventive Medicine*, *10*(2), 77-84. [https://doi.org/10.1016/S0749-3797\(18\)30622-6](https://doi.org/10.1016/S0749-3797(18)30622-6)
- Braitman, A. L., & Henson, J. M. (2016). Personalized boosters for a computerized intervention targeting college drinking: The influence of protective behavioral strategies. *Journal of American College Health*, *64*(7), 509-519. <https://doi.org/10.1080/07448481.2016.1185725>
- Braitman, A. L., & Lau-Barraco, C. (2018). Personalized boosters after a computerized intervention targeting college drinking: A randomized controlled trial. *Alcoholism: Clinical and Experimental Research*, *42*(9), 1735-1747. <https://doi.org/10.1111/acer.13815>

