Statistical Analysis Plan

Timing Personalized Feedback After Alcohol Health Education (TIME)

NCT04453007

11/13/2020

Statistical Analysis Plan

Prior to hypothesis testing, the data will be examined for normality and outliers. Histograms and values for skewness and kurtosis will be examined. Positively skewed variables will be natural log transformed, unless paired with an excessive number of zeroes. If there are an excess of zeroes in an outcome, the variable will be dichotomized if other values are not well represented, or appropriate modeling techniques will be used (e.g., hurdle models) if other values are well represented. Boxplots will be used to check for outliers. Extreme values will be winsorized (i.e., cases retained in the sample, but values made less extreme). Cases with missing data will be compared to complete cases across major study variables to identify if there are systematic differences in missingness. If significant associations are identified, these variables will be used as covariates in later analyses.

To address the major aim of the study, the data will be analyzed using latent growth models within a structural equation modeling framework. Separate models will be conducted for each alcohol outcome: alcohol consumption (e.g., quantity), and alcohol-related problems. It is not known the exact trajectory across time (baseline, 1 month, 3 months, 6 months, 9 months), so a few models will be compared to identify which best captures the shape of change over time. A simple model that reflects change to 1 month (slope 1; initial change post-intervention) and longer-term maintenance (slope 2; linear growth to 9 months) will be compared to models with additional piecewise slopes or curvilinear components in case longer-term maintenance is not a linear process. Study condition (6 groups) will be dummy coded across 5 variables with “no booster” as the category of reference, and will serve as a predictor of each latent variable (latent intercept, each slope). All models will be conducted using maximum likelihood estimation, and will control for gender. The model for problems will also control for alcohol quantity.

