Given prior findings that emailed booster feedback containing personalized normative feedback and protective behavioral strategies (PBS) was significantly more effective for select groups (i.e., those lower in PBS use [Braitman & Henson, 2016], legal age drinkers [Braitman & Lau-Barraco, 2018]), we will examine potential moderators of booster efficacy as a supplementary exploratory analysis. Legal drinking status by age (coded as 1 = *age 21-24* [legal], 0 = *age 18-20* [underage]) and baseline PBS use (in its original continuous metric) will be explored as potential moderators. For each outcome, two additional models will be conducted (one for each moderator). The moderator will be added as a predictor of each latent factor (latent intercept, slope 1, and slope 2). Multiple interaction terms will be created to capture the interaction with condition (dummy coded across 5 variables). These interaction terms will also be included as predictors of each latent factor. Thus, the outcome at baseline and change over time will be predicted by condition, the moderator, and the interaction between the two, controlling for relevant covariates.

References:

- Braitman, A. L., & Henson, J. M. (2016). Personalized boosters for a computerized intervention targeting college drinking: The influence of protective behavioral strategies. *Journal of American College Health, 64*(7), 509-519.
<http://doi.org/10.1080/07448481.2016.1185725>
- Braitman, A. L., & Lau-Barraco, C. (2018). Personalized boosters after a computerized intervention targeting college drinking: A randomized controlled trial. *Alcoholism: Clinical and Experimental Research, 42*(9), 1735-1747.
<http://doi.org/10.1111/acer.13815>

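### The all-times arm is there for a repeated-administration comparison, but the SAP tests it only against no booster, so as written it does not test whether four boosters do more than one

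*Protocol*

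**What the plan says.** The protocol (Primary Aims) sets out six conditions: a booster at week 2, 6, 10 or 14, at all four times, or not at all. On the all-times arm it says: "A fifth group will receive the booster at all four delivery times as a repeated administration comparison". It does not name the comparator. The overall aim is given as timing: "the aim of the current study is to identify optimal timing for sending the tailored booster feedback via booster email".

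The SAP (paragraph on latent growth models) says: "Study condition (6 groups) will be dummy coded across 5 variables with “no booster” as the category of reference". These variables enter the model as follows: "will serve as a predictor of each latent variable (latent intercept, each slope".

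The exploratory moderator paragraph keeps the same coding: "Multiple interaction terms will be created to capture the interaction with condition (dummy coded across 5 variables".

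Neither document names a contrast of the all-times arm with any single-booster arm or with their average. Neither gives a change of reference group, an omnibus test of condition, or a multiplicity rule. The protocol's power statement, in the section on the participant population, concerns booster effects in general and does not say which contrast was simulated.

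**The concern.** A repeated-administration arm is informative about repetition only when it is set against single administration. The coefficient the SAP will estimate for that arm answers a different question, whether four boosters beat none.

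With only comparisons against control on the page, the easiest reading of the results is that one schedule was significant and the other was not. That pattern does not test repetition, and it arises often when the two schedules work equally well. A four-email schedule could be recommended or dismissed on this basis. Under equal allocation, which the protocol does not state, about one sixth of participants are in the arm concerned.

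**Working it through.** **Which comparisons are planned.** Six arms give 6 × 5 / 2 = 15 pairs. Five dummies against one reference cover 5 of them. None of the 5 is between two booster arms.

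**The plan's own figure.** The protocol gives N = 180 for power of .80+ with 24% attrition. This cannot be reproduced, because the variances, covariances, alpha, predictor coding and contrast behind the simulation are not given. Nothing below depends on that figure being right or wrong.

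**How often significance patterns disagree when the true effects are equal.** Assume equal arms, two-sided 0.05 and normal estimates, and ignore rejections in the opposite tail. Two estimates that share one control arm each have variance 2σ²/n and covariance σ²/n, so their correlation is 0.5. If each has power p, then P(exactly one significant) = 2 × (p − P(both significant)).

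- p = 0.50: P(both) = 1/4 + arcsin(0.5)/(2π) = 0.333, so 2 × (0.50 − 0.333) = 0.33.
- p = 0.80: P(both) = 0.687 from the bivariate normal, so 2 × (0.80 − 0.687) = 0.23.
- p = 0.90: P(both) = 0.832, so 2 × (0.90 − 0.832) = 0.14.

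The 33% is the peak. The range over these powers is 14% to 33%.

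**Which assessments can show a repetition effect.** At about 4.35 weeks per month, the assessments at 1, 3, 6 and 9 months fall at about weeks 4.3, 13.0, 26.1 and 39.1. At 1 month the all-times arm has received only the week-2 booster. At 3 months its week-14 booster is still to come. Only the 6- and 9-month assessments follow the full schedule, so the slope to 1 month cannot carry a repetition effect.

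**Time since the last booster at 6 months.**

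- All-times arm: 26.1 − 14 = 12.1 weeks.
- Single arms (weeks 2, 6, 10, 14): 24.1, 20.1, 16.1 and 12.1 weeks, an average of 18.1.

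The 14-week arm is the only single arm that matches the all-times arm on recency. The difference between those two arms is therefore the effect of adding the three earlier boosters. A contrast with the pooled single arms carries a 6-week difference in recency, at 6 months and equally at 9 months (25.1 against 31.1).

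**Can the planned model supply the contrast?** Yes. In simulated data with the SAP's dummy coding (least squares, 30 per arm), the all-times coefficient minus the mean of the four single-booster coefficients equalled the difference in group means (−0.248 both ways).

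**Precision.** Equal allocation gives 180 / 6 = 30 per arm, and 76% retention leaves 22.8. In SD units, treating the contrast as a simple comparison of means:

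- All-times minus 14-week: √(2/22.8) = 0.296 (0.258 before attrition).
- All-times minus the four single arms pooled: √(1/22.8 + 1/91.2) = 0.234 (0.204 before attrition).

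**Illustrative power.** Read the protocol's 0.537 as a standardised mean difference, two-sided 0.05, with 22.8 per arm. If four boosters beat one by the full 0.537 SD, power is 0.44 pairwise and 0.63 pooled. At half that difference it is 0.15 and 0.21. Other readings of the coefficient give other values: if it is fully standardised on a one-in-six dummy, power for half the booster effect is 0.19 to 0.41 pairwise and 0.28 to 0.59 pooled, for slope reliability of 0.2 to 0.5.

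**The case against.** A reader might infer that the trial cannot say whether four boosters do more than one. The documents do not support that. The arms are randomised, the data will be collected, and the contrast follows from coefficients the SAP already estimates. What is missing is a prespecified contrast.

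It can also be said that:

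- **The comparator is inferred.** The protocol does not say that the all-times arm is to be compared with single delivery. This stands, although it is the natural reading. All-times against none is a valid test, so the arm is not wasted.
- **The harm is conjectural.** No passage plans to argue from which arm is significant. That is true, but the SAP offers nothing else on repetition.
- **The stated aim is timing, and the same coding sentence leaves the four timing arms uncompared with each other.** This is a fair point about the root cause. Contrasts among the single timings would still not supply the repetition contrast, so it has to be named separately.
- **The pooled contrast mixes number with recency, and the pairwise contrast is no more precise than the planned tests.** Both points stand, and they decide which contrast is main and which is secondary.
- **Power for four against one may be low.** This stands. It argues for intervals and against reading a null as equivalence. It does not argue for leaving the contrast out.

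**Conclusion.** The concern holds in this form: the all-times arm is included for a repeated-administration comparison, and the SAP as written tests it only against no booster. A difference in significance against the shared control is not evidence about repetition, since it would occur in about 14% to 33% of trials with equal true effects (power from 90% down to 50%).

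That range assumes equal arms and two-sided 0.05; the documents give neither the allocation ratio nor alpha. The standard errors assume equal allocation and attrition spread evenly over the arms. They are simple two-group approximations, not output from the growth model. The power figures also depend on how the protocol's standardised coefficient is read. None of this shows that N = 180 is wrong for the contrast that was simulated. It shows only that the documents do not establish power for four boosters against one.

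**What to change.** Add to the SAP, for each outcome, on the model-implied value at 6 and 9 months:

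1. **Main repetition contrast:** all-times arm minus 14-week arm.
2. **Secondary contrast:** all-times arm minus the average of the four single-booster arms, with a statement that it mixes number with recency (about 12 against an average of 18 weeks since the last booster at 6 months).

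Report both with confidence intervals. Base any statement on repeated versus single delivery on these contrasts, not on which arm is significant against control. State that a null result will not be read as equivalence. If an outcome is log-transformed, dichotomised or fitted with a hurdle model, as the SAP allows, form the same contrasts on that model's scale.

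The cost is SAP wording and up to 2 contrasts × 2 time points × 2 outcomes = 8 additional contrasts, to be covered by whatever multiplicity control is adopted. No new data or design change is needed. Precision will be limited, at about 0.30 SD (pairwise) and 0.23 SD (pooled), and the SAP should say so.

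### Eligibility criterion 4 was replaced on 3/29/21, but no SAP model includes enrolment cohort: a small, cheaply avoided loss of precision, not a bias

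*Protocol*

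**What the plan says.** **Protocol, Participant population.** Criterion 4 exists in two forms. Under the old rule, students were eligible if they "prior to 3/29/21] were enrolled in classes that were in-person or hybrid [had an in-person component". Under the new rule, they must "after 3/29/21] have consumed alcohol in person with others in the past 30 days". The Protocol describes the old rule as indirect: "Attending classes in person was viewed as a proxy for willingness to gather with others in person". It gives slow enrolment and the small number of students in physical classrooms as reasons for the change. It then says "Thus, we decided to switch to a more direct assessment of social drinking, including enrolling", and the sentence goes on to name those newly admitted: "online students in the study if they reported drinking alcohol with others in person". The other criteria (a drink in the past 2 weeks, age 18-24, undergraduate at the host institution) apply throughout.

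**Protocol, Study Procedure.** The baseline survey assigns each participant at random to one of six conditions. No stratification is described.

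**SAP.** The SAP is dated 11/13/2020, about four and a half months before the switch. The Protocol is dated June 23, 2022. No later SAP is among the documents. Five condition dummies predict the latent intercept and each slope. On covariates the SAP says "All models will be conducted using maximum likelihood estimation, and will control for gender", and then "The model for problems will also control for alcohol quantity". Variables found to be associated with missingness may be added. Legal drinking age and baseline use of protective strategies are exploratory moderators. Enrolment cohort, enrolment date and class format are not named as covariate, moderator, stratum or sensitivity analysis.

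**The concern.** The two rules select on different traits. The old one could admit students who drink alone and shut out online students. The new one requires recent social drinking and lets online students in. The second trait lies in the same domain as the outcomes, and the two enrolment periods also fall in different phases of the pandemic. Level of drinking, or its course over 1 to 9 months, could therefore differ between cohorts.

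If it does, a model without a cohort term treats that difference as unexplained variation. The arms are small (about 30 each if 180 is split equally, about 23 after the planned attrition), so cohort mix will differ between arms by chance. The aim is to find the best of several delivery times, so precision of the arm contrasts matters. The SAP could not have anticipated the change, but nothing in the documents shows that it was revisited.

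**Working it through.** **Plan's own figures.** The plan gives no figure on this point. Its N = 180 is used below only as an input. It cannot be reproduced from what is stated, because alpha, the tested contrast and the variances are not given. The point does not depend on it.

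**Inputs from the Protocol.** N = 180, six conditions, 76% retention. With equal allocation (assumed): 180/6 = 30 per arm, and 30 × 0.76 = 22.8 retained.

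**Assumed inputs, not in the documents.** p = share enrolled under the old rule, 10% to 50%. c = cohort difference in an outcome or growth factor, in within-cohort SD units: 0.5 as the central value, 0.2 to 0.8 as the range.

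**Step 1: bias and type I error.** Arm is assigned by one mechanism regardless of cohort, so cohort is independent of arm by design. A simulation of a simple two-arm comparison of means (40,000 trials, 23 per arm, p = 0.3, c = 0.8, no cohort term, 5% two-sided test) gave type I error 0.051 and mean bias 0.000.

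**Step 2: precision.** Without a cohort term the variance is multiplied by 1 + p(1−p)c², and the standard error by the square root of that. Example: p = 0.5, c = 0.5 gives 1 + 0.25 × 0.25 = 1.0625; √1.0625 = 1.031.

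| p | SE inflation, c = 0.2 | c = 0.5 | c = 0.8 |
|---|---|---|---|
| 10% | 0.2% | 1.1% | 2.8% |
| 20% | 0.3% | 2.0% | 5.0% |
| 30% | 0.4% | 2.6% | 6.5% |
| 50% | 0.5% | 3.1% | 7.7% |

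In sample-size terms, p(1−p)c² runs from 0.4% to 16.0% over the table and is 6.2% at p = 0.5, c = 0.5. In that central case a contrast with 80% power unadjusted would have about 82.3% with the cohort term.

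**Step 3: chance imbalance.** Simulated random allocation of 180 participants to six arms of 30 (20,000 runs):

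| p | SD of booster-minus-control share | One named contrast off by ≥ 20 points | At least one of five off by ≥ 20 points |
|---|---|---|---|
| 10% | 0.08 | 2% | 7% |
| 20% | 0.10 | 7% | 26% |
| 30% | 0.12 | 12% | 39% |
| 50% | 0.13 | 16% | about 47% |

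A 20-point imbalance shifts a contrast by 0.20 × c: 0.20 × 0.5 = 0.10 SD.

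**Step 4: yardstick.** The standard error of a two-arm contrast in SD units is √(2/30) = 0.26 at enrolment and √(2/22.8) = 0.30 after attrition. The 0.10 SD shift is therefore 0.10/0.26 = 0.39 to 0.10/0.30 = 0.34 standard errors.

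**Step 5: no double counting.** Steps 2 and 3 describe one effect. The unadjusted standard error already includes the variation that chance cohort imbalance produces. The two sizes should not be added.

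**The case against.** The strongest reply is that nothing is invalid here. Randomisation makes the unadjusted contrasts unbiased, their standard errors cover chance imbalance, and eligibility changes in mid-trial are common. That stands.

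A reader might infer that pooling the cohorts confounds the timing comparison, or that a cohort imbalance could readily reorder the arms. The documents do not support either. Every arm is filled by the same random mechanism in both periods. On ordering, suppose one booster arm is truly better by 0.537 SD (the Protocol's β read as a mean difference in SD units), the other four are equal, and 22.8 are retained per arm. The better arm then ranks first about 89.5% of the time with cohort accounted for. Without it the figure is about 88.3-88.8% at c = 0.5 with shares of 20-50%, and about 86.5% at c = 0.8 with a 50% share. The loss is one to three percentage points.

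Other replies also have weight:

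- The old-rule share may be small, given that enrolment was slow and few students attended in person. At 5% the SE inflation at c = 0.5 is 0.6%.
- The cohorts overlap: a student attending in person who drinks with others qualifies under either rule. No document shows a difference in drinking between them.
- A pure difference in level goes mainly into the intercept factor. Slope contrasts, which carry the booster effect, are affected mainly if the cohorts differ in change over time. The upper end of the range is a worst case.

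One reply does not stand: that the missing-data rule already covers cohort. It would do so only if cohort were counted among the major study variables and proved to be associated with missingness. The SAP does not name it.

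**Conclusion.** The point holds as a modest one about precision. Criterion 4 changed, the available SAP predates the change, and no model takes account of it. The cost is about 1-3% on the standard error of a contrast at a 0.5 SD cohort difference and old-rule shares of 10-50%, rising to about 8% at 0.8 SD and a 50% share. A 20-point imbalance in one contrast is worth about a third of a standard error. There is no systematic bias and no type I error inflation.

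These sizes rest on an unstated cohort split, an unstated cohort difference, equal allocation, and a simple comparison of means standing in for the latent growth model. If the split is very uneven or the cohorts follow similar courses, the effect is negligible. The case for acting is that the remedy is nearly free, not that the planned analysis is unsound.

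**What to change.** Issue a dated SAP update before outcome analysis that:

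1. adds a binary indicator for enrolment before or after 3/29/21 as a predictor of the intercept and each slope, in both the consumption and the problems models;
2. reports the number enrolled under each rule, by arm.

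The cost is some SAP wording and one parameter per growth factor in each model. The indicator follows from the baseline date, so no new data are needed. Timing matters: if it is added after outcomes have been examined, it becomes a post-hoc choice.

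The update should state that the indicator captures the criterion change and the pandemic phase together and cannot separate them. If estimates are also shown for the new-rule cohort alone, label them descriptive and do not use them to rank timings. With old-rule shares of 20-50% that cohort would have only 30 × 0.8 = 24 down to 30 × 0.5 = 15 per arm before attrition.
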